5.3 Pharmacokinetics

Unless otherwise stated, PK analysis will be performed on the PKS.

5.3.1 Analysis of Concentration Measures

The plasma concentration-time profiles will be summarized for Part A by formulation and gastric condition, and for Part B by dose level and group using descriptive statistics (number of available observations, arithmetic mean, sd, geometric mean, geometric coefficient of variation (geometric cv), median, IQR, minimum, and maximum).

Individual concentration-time profiles will be displayed graphically on a linear-linear scale and semilogarithmic scale. For Part A, individual concentration-time profiles for a given formulation and gastric condition will be presented on the same plot; for Part B, individual concentration-time profiles will be presented separately for each participant (both doses on the same plot).

Overall geometric mean plasma concentrations-time curves and corresponding 95% CIs will be displayed for Part A by formulation and gastric condition, and for Part B by dose level and participant group.

Individual concentrations will be listed for Part A by formulation and gastric condition, and for Part B by dose level and participant group.

Standard reporting procedures of individual values and descriptive statistics for plasma concentration data in listings, tables, and figures are described in Appendix 2 (Section 6.2.1).

5.3.2 Pharmacokinetic Parameters

The following PK parameters will be determined using the actual recorded sampling times and non-compartmental method(s) with Phoenix WinNonlin® (Version 8 or higher), as applicable: C_{max} , t_{max} , AUC_{last} , AUC_{inf} , $AUC\%Extrap$, $t_{1/2}$, Lambda z (λ_z), CL/F (UCB0599 only), Vz/F (UCB0599), MRC_{max}, and MRAUC_{inf} from the plasma concentration-time data.

Table 5-6: Non-compartmental PK parameters for UCB0599 in plasma

PK Parameter	Definition
AUC _{inf}	The AUC from time zero to infinity (mass * time * volume ⁻¹).
AUC _{last}	The AUC from time zero to the last measurable drug concentration sampling time (t _{last}) (mass * time * volume ⁻¹).
C _{max}	The maximum (peak) observed drug concentration following a single dose administration (mass * volume ⁻¹).
t _{max}	The time to reach maximum (peak) drug concentration following a single dose administration (time).
t _½	The elimination half-life associated with the terminal slope (λ_z) of a semilogarithmic concentration-time curve (time).
CL/F ^a	The total apparent body clearance of drug (volume/time).
Vz/F ^a	The apparent volume of distribution during terminal phase (associated with λ_z) (volume).
Lambda_z (λ_z)	Terminal elimination rate constant (1/time).
AUC%Extrap ^b	Area under the <matrix> concentration-time curve extrapolated from the time t to infinity as a percentage of total AUC.
Rsq_adj ^c	Square of the correlation coefficient (adjusted for the number of data points included) associated with λ_z .
MRC _{max} ^d	C _{max} metabolite to parent ratio.
MRAUC _{inf} ^d	AUC _{0-inf} metabolite to parent ratio.

^a For UCB0599 only

^b AUC%Extrap is listed if AUC_{inf} is presented

^c Rsq_adj is listed only

^d Metabolites only

PK parameters of UCB0599 will be listed and summarized using descriptive statistics similarly to the plasma concentrations.

Standard reporting procedures of individual values and descriptive statistics for PK parameters in listings, tables, and figures are described in Appendix 2 (Section 6.2.2).

5.4 PK Endpoints Analysis

5.4.1 Definition of endpoint(s)

PK endpoints are based on the definitions in Table 5-6.

The primary endpoints for PK objectives in both parts are:

- AUC_{0-t}
- AUC_{inf}
- C_{max}

The other PK endpoints for Part A are defined as follows:

- For UCB0599:
 - t_{max} , $t_{1/2}$, CL/F, and Vz/F (if possible but not limited)
- For [REDACTED] metabolites:
 - C_{max} , t_{max} , AUC_{0-t} , and AUC_{inf}
 - metabolite/parent C_{max} and AUC ratio (corrected for the molecular weight of the entities), as appropriate

The other PK endpoints for Part B are defined as follows:

7. For UCB0599:
 - t_{max} , CL/F, Vz/F, $t_{1/2}$, $C_{max}/BW/D$, $AUC_{0-t}/BW/D$, and $AUC_{inf}/BW/D$
- For [REDACTED] metabolites:
 - C_{max} , t_{max} , AUC_{0-t} , and AUC_{inf}

5.4.2 Part A

5.4.2.1 Analyses required for Primary Objective (on Primary PK endpoints)

The 2 new UCB0599 formulations will be compared with reference ‘granules in capsule’ formulation and compared against each other under normal gastric pH condition, and under elevated gastric pH condition, separately. The primary comparisons of interest are:

- non-encapsulated tablets vs granules in capsule under normal pH condition
- encapsulated tablets vs granules in capsule under normal pH condition
- non-encapsulated tablets vs granules in capsule under elevated pH condition
- encapsulated tablets vs granules in capsule under elevated pH condition
- non-encapsulated tablets vs encapsulated tablets under normal pH condition
- non-encapsulated tablets vs encapsulated tablets under elevated pH condition

In order to estimate these comparisons, the primary analysis model will be applied to the 2 sets of data separately; namely, the data under normal gastric pH condition (first 3-period crossover design substudy, ie substudy 1) and the data under elevated gastric pH condition (second 3-period crossover design substudy, ie substudy 2).

The PK parameters C_{max} , AUC_{0-t} , and AUC_{inf} will be evaluated according to a univariate model of analysis of variance (ANOVA), adapted to crossover designs. The model will include a random intercept term for participant within sequence and fixed effect categorial terms for sequence, period, and formulation (Model 1.1 and Model 1.2 in Table 6-10).

The dependent variables will be logarithmically transformed by natural logarithms (\ln) prior to statistical testing, following the usual recommendations.

The linear mixed model is given as following:

$$\ln(Y) = Q + S_i + P + T + \varepsilon, \text{ where} \quad (1)$$

- $\ln(Y)$ is the log transformed PK parameter value,

- Q is the fixed effect term for the sequence,
- S_i is the fixed effect term of the participant nested to the sequence,
- P is the fixed effect term for the period,
- T is the fixed effect term for the treatment,
- ε is the random error.

The PROC MIXED procedure in the Statistical Analysis Software (SAS) will be used for this analysis. For estimation based on a linear mixed model, covariance matrix applied to the within-subject error will be estimated by restricted maximum likelihood (REML). The Kenward-Roger approximation will be used to estimate the degree of freedom. Variance component structure will be used as covariance in this linear mixed model.

For each PK parameter and set of substudy data separately (ie, gastric pH condition), the least square mean (LSMEAN) for each formulation and 95%CI of LSMEANS, difference in LSMEANS between the each formulation, and corresponding 90% confidence interval (CI) will be calculated. These values will then be back-transformed to give the estimate of the geometric mean ratio (GMR) for the non-encapsulated tablets versus granules in capsule, the GMR for the encapsulated tablets versus granules in capsule, and the GMR for the non-encapsulated tablets versus encapsulated tablets, alongside with their corresponding 90% CI.

The estimates of the geometrics mean ratios with their corresponding 90% CI will be displayed in a summary plot.

Additionally, the between-participant CVs available for single formulation at given gastric pH condition may be calculated.

5.4.2.2 Sensitivity required for Primary Objective (on Primary PK endpoints)

The analysis described in [Section 5.4.2.1](#) will be performed on the PK parameters separately to the data for each formulation in comparison to the reference formulation in separate mixed model procedure (Model 1.1a, Model 1.1b, Model1.2a, and Model 1.2b in [Table 6-10](#)).

5.4.2.3 Analyses required for Other Objective (on Primary PK endpoints)

Another objective of the study is to estimate the relative bioavailability of UCB0599 under elevated gastric pH versus normal gastric pH for each tested formulation.

- granules in capsule under elevated pH condition vs granules in capsule under normal pH condition
- non-encapsulated tablets under elevated pH condition vs non-encapsulated tablets under normal pH condition
- encapsulated tablets under elevated pH condition vs encapsulated tablets under normal pH condition

To that effect, a supplementary analysis will be performed using the PK parameters (C_{max} , AUC_{0-t} , and AUC_{inf}) where all 3 formulation data from all 6 periods (normal and elevated gastric pH data) will be combined into a single linear mixed model a random intercept term for participant within sequence and with fixed effect categorical terms for sequence, gastric status, formulation,

formulation (nested to the gastric condition), and period within substudy (ie, 3-level categorical variable) (Model 2.1 in [Table 6-10](#)).

The linear mixed model is given as following:

$$\ln(Y) = Q + S_i + G + T + T_g + P + \varepsilon, \text{ where} \quad (2)$$

- $\ln(Y)$ is the log transformed PK parameter value,
- Q is the fixed effect term for the sequence,
- S_i is the fixed effect term of the participant nested to the sequence,
- G is the fixed effect for the gastric status,
- T is the fixed effect term for the formulation,
- T_g is the fixed effect for the formulation nested to gastric status,
- P is the fixed effect term for the period,
- ε is the random error.

The MIXED procedure in SAS software will be used for this analysis. For estimation based on a linear mixed model, covariance matrix applied to the within-subject error will be estimated by restricted maximum likelihood. The Kenward-Roger approximation will be used to estimate the degree of freedom. Variance component structure will be used as covariance in this linear mixed model.

For each PK parameter and formulation, the LSMEAN for elevated gastric pH and normal gastric pH and corresponding 95%CI, difference in LSMEANs between the elevated gastric pH and normal gastric pH, and corresponding 90% CI will be calculated. These values will then be back-transformed to give the estimate of GMR for elevated gastric pH versus normal gastric pH, alongside with their corresponding 90% CI.

The ratios and corresponding 90% CIs will be obtained for the granules in capsule, non-encapsulated tablet, or encapsulated tablet under elevated gastric pH condition versus the respective formulation under normal gastric pH condition and displayed in a summary plot.

5.4.2.4 Sensitivity required for Other Objective (on Primary PK endpoints)

The analysis described in Section [5.4.2.3](#) will be performed on the PK parameters separately to the data for each formulation when comparing pH condition (Model 2.1a, Model 2.1b, and Model 2.1c in [Table 6-10](#)).

5.4.2.5 Analyses required for Other Objective (on Other PK endpoints)

The other PK parameters of UCB0599 and metabolites will be summarized by formulation and gastric condition using descriptive statistics as described in Section [5.3.1](#).

- For UCB0599: t_{\max} , $t_{1/2}$, CL/F, and Vz/F (if possible but not limited). For t_{\max} , only the median, IQR, minimum, and maximum will be reported.

- For **CCI** metabolites: C_{max} , t_{max} , AUC_{0-t} , AUC_{inf} , and each metabolite/parent C_{max} and AUC ratio (corrected for the molecular weight of the entities), as appropriate.

$$MR_C_{max} = \frac{C_{max}(\text{metabolite})}{C_{max}(\text{parent})} * \frac{\text{Molecular weight (parent)}}{\text{Molecular weight (metabolite)}}$$

$$MR_AUC_{inf} = \frac{AUC(\text{metabolite})}{AUC(\text{parent})} * \frac{\text{Molecular weight (parent)}}{\text{Molecular weight (metabolite)}}$$

where,

Molecular weight (parent) = 425.59 g/mol

CCI

5.4.3 Part B

5.4.3.1 Analyses required for Primary Objective (on Primary PK endpoints)

Dose proportionality for C_{max} , AUC_{0-t} , and AUC_{inf} will be examined for each participant group (Table 5-3) via the power model

$$Y = \alpha + dose^{\beta}, \quad (3)$$

where α is the subject random intercept, Y is the parameter of interest, and β is the slope. The PK parameters and the dose will be logarithmically transformed prior to analysis. The power model will be estimated by regressing the log-transformed PK parameter onto the log-transformed dose.

$$\ln(Y) = \alpha + \beta * \ln(dose) \quad (4)$$

The power model will be fitted by restricted maximum likelihood (REML) using the PROC MIXED procedure in SAS, with a fixed effect term for dose level and a random effect for participant. A lack of fit test will be performed to check the linearity assumptions for appropriateness of the power model. An unstructured covariance matrix will be specified for the participant random effect. If the model fails to converge, other covariance matrices such as VC and CS may be considered.

The results of the power model will be reported after back-transformation, including the estimated dose proportionality parameter β along with corresponding 90% CI (slope ≈ 1 implies dose proportionality).

Graphical displays including observed values, regression line of the fitted values with the 90% CI will be provided for each log-transformed PK parameter vs. log-transformed dose.

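### SAP 5.4.3.1 lists the power-model slope β among the back-transformed results yet judges it against 1, and the two instructions are incompatible

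*SAP*

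**What the plan says.** SAP 5.4.3.1 sets out the dose-proportionality analysis of Cmax, AUC0-t and AUCinf in Part B. It states that "Y is the parameter of interest, and β is the slope", and that "The power model will be estimated by regressing the log-transformed PK parameter onto the log-transformed dose". Equation (4) writes this as ln(Y) = α + β·ln(dose).

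On reporting, it says: "The results of the power model will be reported after back-transformation, including the estimated dose proportionality parameter β", together with a 90% CI. The same sentence closes with the criterion in brackets: "slope ≈ 1 implies dose proportionality".

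Two smaller items sit in the same section. Equation (3), given as the power model before logs are taken, adds α to dose^β instead of multiplying. The fitting sentence describes a model "with a fixed effect term for dose level and a random effect for participant".

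**The concern.** In equation (4) β is a unitless exponent. It describes exposure on the original scale already: exposure is proportional to dose raised to the power β. What sits on the log scale, and needs exponentiating, is the intercept and the fitted means. The reporting sentence nevertheless names β and its CI among the results to be back-transformed, then sets a benchmark that is valid only for β untransformed.

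If the sentence is programmed as written, the printed slope and interval cannot be compared with the stated benchmark. A value near 1 in the table would be read as proportionality when it would mean no dose response. The section is headed as the required analysis for the Part B primary objective, and Protocol 4.3 says the three doses were spaced by a common ratio of 2 partly to evaluate dose proportionality.

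**Working it through.** **Inputs**
- Model: ln(Y) = α + β·ln(dose) (SAP 5.4.3.1, equation 4).
- Benchmark: slope about 1 (SAP 5.4.3.1).
- Doses: 90, 180 and 360 mg, a 4-fold range (SAP 1.2.2).
- Log base: natural. Equation (4) uses ln, and SAP 5.4.2.1 says "The dependent variables will be logarithmically transformed by natural logarithms".
- Meaning of back-transformation: exponentiation of ln-scale estimates. For the Part A differences in least-squares means, SAP 5.4.2.1 says "These values will then be back-transformed to give the estimate of the geometric mean ratio (GMR"); SAP 5.4.3.2 likewise ends with an exponential transformation.

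**Step 1: reproduce the benchmark.** If Y = c·dose, then ln(Y) = ln(c) + 1·ln(dose), so β = 1. The benchmark of 1 is correct for β untransformed.

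**Step 2: apply the reporting sentence literally.** The printed value is exp(β).

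| True relation | 360/90 mg exposure ratio, 4^β | β | exp(β) |
|---|---|---|---|
| Proportional | 4.00 | 1.00 | 2.72 |
| Square-root rise | 2.00 | 0.50 | 1.65 |
| No rise with dose | 1.00 | 0.00 | 1.00 |

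**Step 3: look for another back-transformation that gives 1 at proportionality.** At β = 1, 10^β = 10 and 2^β (fold change per doubling) = 2. Only 4^(β−1), the dose-normalised 360/90 mg ratio, equals 1, and the SAP does not describe it. Protocol 9.4.2.2 uses dose-normalised data with a slope compared with zero. Exponentiating a zero slope gives 1, but equation (4) is not dose-normalised, so that does not rescue the wording. SAP 6.4 records no change from the protocol's analyses.

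**Step 4: illustrate the interval.** No residual variance is given for Part B. As an assumption, take the Part A planning value for Cmax, σ² = 0.0782 (SAP 3.1). Each origin has 12 participants on active drug, four in each of the sequences 90→180, 180→360 and 360→90 mg, so the within-participant differences in ln(dose) are +ln2, +ln2 and −2·ln2.
- Sum of squares: (4·1 + 4·1 + 4·4)·(ln2)² = 24·(ln2)² = 11.53.
- SE(β) = sqrt(2·0.0782 / 11.53) = 0.116.
- 90% half-width with 11 df: 1.796 × 0.116 = 0.209.
- At an estimate of 1, the CI for β is 0.79 to 1.21. Exponentiated it is 2.21 to 3.35.

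Range: the half-width scales with the square root of σ². Half the variance gives 0.148, so 0.85 to 1.15 becomes 2.34 to 3.15. Double gives 0.296, so 0.70 to 1.30 becomes 2.02 to 3.65. For the exponentiated interval to reach 1, the lower limit for β would have to reach 0. That needs a half-width of 1, which is 1/0.209 = 4.8 times larger, or about 23 times the variance.

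A REML simulation of the same layout under true proportionality agrees. It used σ² = 0.0782, assumed between-participant variances of 0.05, 0.10 and 0.20, normal quantiles and 600 data sets in all. Average intervals for β ran from about 0.81 to 1.18, and no exponentiated interval contained 1.

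**Step 5: equation (3).** The logarithm of α + dose^β is not α + β·ln(dose). Equation (4) follows from Y = exp(α)·dose^β.

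**The case against.** The strongest reply is that the sentence corrects itself. The SAP defines β as the slope and ends the sentence with a benchmark for the slope, which fixes the untransformed scale. An experienced programmer could well leave β alone and print 1. That stands: the 2.72 is conditional on a literal reading. It does not remove the defect, because the sentence expressly includes β and its CI in what is back-transformed and nothing exempts them.

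A reader might infer that the SAP will reverse the proportionality conclusion. The documents do not support that. SAP section 2 lists no hypotheses, Protocol 9.4.2.2 plans no formal comparison in Part B, and the benchmark is a descriptive guide. The planned plots of log exposure against log dose, and the summaries by dose, would probably expose an error: 2.72 read as an exponent would imply 4^2.72, about a 43-fold rise over a 4-fold dose range. Taking logs of the printed value would recover β.

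A reader might also infer that this is the only model for the Part B primary PK objective. It is not: SAP 5.4.3.2 gives an exploratory ANOVA and 5.4.3.3 a sensitivity analysis.

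Finally, because Table 5-4 lists dose level as categories, a reader might infer that the model is fitted by category and yields no β. The log-log regression sentence, the lack-of-fit check for linearity and the planned regression line all rule that out. Table 5-4 defines grouping variables for outputs, and one of its levels is pooled placebo, which has no ln(dose). The wording is loose, no more. Similarly, equation (3) is not what is fitted, and because the text was extracted from PDF a misread operator cannot be excluded.

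**Conclusion.** The reporting instruction is wrong as written: it cannot be satisfied together with its own benchmark. Followed literally, exact proportionality prints as 2.72 and no rise with dose as 1.00. Those two figures rest only on natural logs and on back-transformation meaning exponentiation, both of which the SAP's own usage supports. The interval illustration (0.79 to 1.21 becoming 2.21 to 3.35) also assumes that the Part A Cmax residual variance applies in Part B. It is not needed for the conclusion.

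The consequence is limited: the sentence contradicts itself and does not mandate one wrong answer, and no decision rule rests on β. It still merits correction, because this is the one Part B primary-objective PK model not labelled exploratory or sensitivity, and its reported scale should not be left to the programmer. Equation (3) and the name of the regressor are tidy-ups.

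**What to change.** Replace the reporting sentence in SAP 5.4.3.1 with one to this effect: *β and its 90% CI are reported untransformed and compared with 1; only the intercept or the fitted geometric means are exponentiated.*

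In the same edit, correct equation (3) to Y = exp(α)·dose^β so that its logarithm is equation (4), and write ln(dose) in place of dose level in the sentence on the model fit.

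The cost is a few words of SAP text, best settled before the Part B tables are programmed. The fitted model, the data and the list of planned outputs do not change. A fold-deviation summary such as 4^(β−1) could be added if wanted, but it would be a new output and is not needed to cure the inconsistency.

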5.4.3.2 Exploratory analysis for Primary Objective (on Primary PK endpoints)

The co-primary PK endpoint data obtained for the groups will be log-transformed. For each dose level, the transformed data will be combined into an ANOVA model with fixed effect terms for participant group. The model may be adjusted for age, height and weight. Therefore, the impact of the Baseline (Day-1) characteristics of age, height and weight will be included in the statistical

model as fixed effect and tested by 10% significant level individually. If a fixed term has a significant effect to the model for all three primary PK parameters at 10% significant level, the term will be included to the ANOVA model as fixed effect. The SAS PROC MIXED procedure will be used. Point estimates for the geometric mean ratios and corresponding 90% CIs will be obtained and compared between the Japanese participants versus the Part A participants (healthy participants on normal gastric condition on the formulation chosen for Part B), and between the Chinese participants versus the Part A using least squares means and root mean squares of error from the model with subsequent exponential transformation.

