#### **9.4.2.2 Part B**

The primary objective of Part B is to evaluate the plasma PK of UCB0599 after administration of a single dose of an oral formulation in healthy participants of Japanese and Chinese origins.

The PK parameters ( $C_{max}$ ,  $AUC_{0-t}$ , and  $AUC_{inf}$ ) will be used to estimate the following:

- PK parameters for the 3 groups (Part A healthy participants, Japanese participants, and Chinese participants)
- Dose proportionality for each group, including graphical presentation

Individual concentration-time profiles will be displayed graphically on a linear-linear scale and semilogarithmic scale.

Overall geometric mean plasma concentration-time curves and corresponding 95% CIs will be displayed by group.

No formal comparison will be made.

The PK analyses will be performed on the PK data from Part B.

The plasma concentration-time profiles and PK parameters of UCB0599 will be summarized by dose level and group using descriptive statistics (number of available observations, arithmetic mean, standard deviation, geometric mean, coefficient of variation of geometric mean, median, minimum, and maximum). Values below the LLOQ will be reported with a clear sign indicating that they were below the LLOQ. Descriptive statistics of concentrations will be calculated if at least two-thirds of the individual data points are quantifiable ( $\geq LLOQ$ ).

Descriptive statistics will be executed for all PK parameters estimated by ethnicity and dose. For  $t_{max}$ , only the median, minimum, and maximum will be reported.

The PK descriptive statistics from Part A healthy participants who receive 180mg dose of the formulation used in Part B will be presented alongside.

Dose proportionality for  $C_{max}$ ,  $AUC_{0-t}$ , and  $AUC_{inf}$  will be examined for each ethnic group and for Part A healthy participants who receive a 180mg dose of the formulation used in Part B and graphically reported. Dose proportionality could be achieved by dose normalization and log-transforming  $C_{max}$  and AUC data, in which a linear regression  $C_{max}$  versus dose and AUC versus dose will be used to assess if the slope of the regression line deviates statistically significantly from zero. If the slope is not different from zero, then it can be concluded that the PK is proportional to dose.

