The co-primary PK endpoint data obtained for the UCB0599 formulation used in Part B at the 180mg dose under normal gastric pH condition for the three ethnicities (ie, N=36 participants from Part A, N=8 participants of Japanese origin, and N=8 participants of Chinese origin) will be log-transformed. As an exploratory analysis, transformed data will be combined into an Analysis

of Variance (ANOVA) model with fixed effect terms for cohort, assuming the data for each ethnicity come from a single parallel arm design. Point estimates for the geometric mean ratios and corresponding 90% CIs will be obtained and compared between the Japanese participants versus the Part A participants, and between the Chinese participants versus the Part A participants using least squares means and root mean squares of error from the model with subsequent exponential transformation.

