1.2.1 Part A

Part A is an open label, randomized, 2 in-series crossover substudies, each with a fixed sequence complete block design of 3 treatment periods in healthy male and female participants.

Part A consists of the following (for a total duration of up to 68 days):

- A 28-day Screening Period (2 to 28 days before administration of study medication)
- A Baseline health status on admission to study site on Day -1.
- 6 treatment periods (each treatment period is followed by a 4-day Washout Period)
 - The first 3 periods include the evaluation of UCB0599 PK following its single-dose administration (180mg) of each formulation under normal gastric pH condition.
 - The second 3 periods include the evaluation of UCB0599 PK following its single-dose administration (180mg) of each formulation under the condition of elevated gastric pH. The elevated gastric pH will be achieved by co-administering esomeprazole 40mg once daily (QD) over the duration of the 3 treatment periods (Day 14 to Day 33; see [Table 1-3](#)).
- A 7-day Safety Follow-Up (SFU) Period

After completion of Part A, an interim analysis will be performed on key PK endpoints for all available PK data, to support the decision on selection of the Part B formulation.

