5.4.3.3 Sensitivity analysis for Primary Objective (on Primary PK endpoints)

The analysis described in Section 5.4.3.2 will be repeated on the normalized PK parameters using the same ANOVA model.

For the C_{max} normalization:

$$C_{max_w} = C_{max} / BW, \text{ body-weight normalization}$$

$$C_{max_d} = C_{max} / Dose, \text{ dose normalization}$$

$$C_{max_wd} = C_{max} / (BW * Dose), \text{ body-weight and dose normalization}$$

(BW=Day -1 bodyweight)

For the AUC_{inf} and AUC_{0-t} similar normalization will be used.

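### The SAP's exploratory comparison with Part A asks for ratios at 90mg and 360mg that cannot be estimated, repeats itself under dose normalisation, and lets a covariate screen absent from the protocol choose which ratio is reported

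*SAP*

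**What the plan says.** **Protocol 9.4.2.2.** The exploratory comparison uses data "at the 180mg dose under normal gastric pH condition for the three ethnicities", with 36 Part A, 8 Japanese and 8 Chinese participants. The analysis is an ANOVA "model with fixed effect terms for cohort, assuming the data for each ethnicity come from a single parallel arm design". No covariates are mentioned. The same section also says "No formal comparison will be made".

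**SAP 5.4.3.2.** The dose restriction is gone: "For each dose level, the transformed data will be combined into an ANOVA model with fixed effect terms for participant group". Ratios with 90% CIs are requested for Japanese versus Part A and Chinese versus Part A. Age, height and weight, labelled as Day -1 values, are each tested at the 10% level. A covariate enters on this condition: "If a fixed term has a significant effect to the model for all three primary PK parameters at 10% significant level".

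**SAP 5.4.3.3.** The analysis "will be repeated on the normalized PK parameters using the same ANOVA model", using division by body weight, by dose, and by both. Weight is defined as "BW=Day -1 bodyweight".

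**SAP 1.2.1.** The normal-pH periods of Part A consist of "single-dose administration (180mg) of each formulation under normal gastric pH condition". No other Part A dose exists.

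**SAP 6.4.** No change from the protocol-planned analyses is declared.

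**The concern.** Three things follow from the text alone. At two of the three dose levels the reference group is empty. Two of the three sensitivity analyses cannot differ from results already produced, so they would suggest a robustness that was not tested. And the trial data decide whether the reported ratio includes or removes any part of the group difference carried by age, height or weight. Those are different quantities, and a reader cannot know in advance which one will appear.

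This is the only planned ratio of the Japanese and Chinese groups to a reference group, in a part described as ethnobridging. What is at stake is how that ratio can be interpreted.

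**Working it through.** **1. Group sizes.** The protocol's Part A assumption reproduces: sqrt(exp(0.0782) - 1) = 28.5%. With n = 36, SE = sqrt(2 x 0.0782/36) = 0.066, 68 df, limits of 0.80 and 1.25, a true ratio of 1.0 and 0.05 per side, TOST power is 91.2%, consistent with the stated 90%. Sequences 2, 4 and 6 have 4 active participants each and each dose occurs in two of them, so there are 8 per dose and origin, as stated.

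**2. Estimability.** Ratios requested: 2 groups x 3 doses x 3 parameters = 18. Estimable at 180mg: 2 x 3 = 6. The other 12 have no Part A observations; only Japanese versus Chinese can be estimated at those doses. With the three normalised repeats, 18 x 4 = 72 ratios are requested. Of these, 12 are both estimable and distinct: 6 raw and 6 per body weight, all at 180mg.

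**3. Duplicates.** Within one dose level, ln(Y/Dose) = ln(Y) - constant. Group differences, standard errors and covariate p-values do not change. In one simulated 180mg data set, raw and Y/Dose both gave 1.017918 (0.800627 to 1.294181). Y/BW and Y/(BW x Dose) both gave 1.275237 (0.960749 to 1.692669).

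**4. The covariate screen.** The documents give no group weights, no exposure-weight relation and no between-participant variance, so what follows is illustrative. Assumptions:
- groups of 36/8/8, Part A mean weight 75kg, weight CV 15%, weights limited to 45-100kg;
- residual SD 0.4, from sqrt(0.0782 + 0.08), where 0.08 is an assumed between-participant variance;
- exposure proportional to weight^-b, and no other ethnic difference;
- correlation 0.8 between parameters, and only weight screened.

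The expected unadjusted ratio is (75/(75 - gap))^b. For b = 0.75 to 1 this is 1.05-1.07 at a 5kg gap and 1.18-1.25 at 15kg. The weight-adjusted ratio is 1.00. Weight enters the model in about 43-70% of trials (29-91% for residual SD 0.5 to 0.3), and in about 3% if weight has no effect.

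Coverage of the nominal 90% CI for Cmax, b = 0.75 to 1, as never adjust / screen / always adjust:

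| Weight gap | Target: weight-adjusted ratio | Target: unadjusted ratio |
|---|---|---|
| 0kg | all 89-90% | all 89-90% |
| 5kg | 87-89 / 89 / 90% | 90 / 86-88 / 87-89% |
| 15kg | 63-74 / 80-82 / 90% | 90 / 69-80 / 67-77% |

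At 8kg the screened interval covers the weight-adjusted ratio about 87% of the time. With a weak effect (b = 0.25), weight enters in about 7-8% of trials and screened coverage of either target stays at about 87-90%, even at 15kg. With b = 0.5 and a gap of 5-8kg it is also 87-90%.

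**5. Weight and height label.** Protocol Tables 1-3 and 1-4 and section 8.2.1 place height and weight at Screening only, and SAP 6.1.1 computes BMI from Screening values. SAP 5.4.3.2 and 5.4.3.3 name Day -1.

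**The case against.** - **No wrong number results at 90mg and 360mg.** This stands. With no Part A rows the software returns no contrast, and the six 180mg ratios are still produced. A reader might infer that erroneous ratios would be reported; the documents do not support that. The defect is an impossible request and an undeclared departure from the protocol.
- **Dose normalisation may have been meant for pooling doses.** This is plausible, since it is the natural way to set 90mg and 360mg data against Part A's 180mg. But the SAP specifies the same per-dose model and states no pooled one. The duplication holds for what is written; clarification is as proper a remedy as deletion.
- **The screen is pre-specified, strict and exploratory.** All true: a covariate must pass for all three parameters, and no decision rule or sample size depends on it. With a strong weight effect and a 15kg gap, the screened interval covers the weight-adjusted ratio better than the protocol's unadjusted model does (80-82% against 63-74%), so the screen is not simply a step backwards. It remains that the screened interval has no fixed target, whereas each fixed model holds about 90% for its own.
- **Large coverage losses are assumption-driven.** This stands. A reader might infer from the 15kg row that the comparison is seriously unreliable; nothing in the documents establishes such a gap or effect.
- **The general baseline rule might settle the weight label.** It does not clearly do so. The rule in SAP 5.1.1.5 gives way where another provision is stated, and these sections state Day -1.
- **Version drift might explain the mismatch.** The SAP was written to the protocol of 02 Mar 2023, but the only change to 9.4.2.2 that Amendment 1 itemises is formulation wording.

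**Conclusion.** The point holds as a specification fault in an exploratory analysis. Three parts need no assumption: 12 of 18 ratios are not estimable, two of three normalised repeats are duplicates under the per-dose model, and the screen and the wider dose scope depart from the protocol without being declared.

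The effect of the screen on interval coverage does rest on assumptions. The loss is about 0 to 4 points with a weak weight effect (exponent 0.25) or a gap of about 5kg or less. It reaches about 10 to 20 points only with exponents of 0.75 to 1 and a gap near 15kg. A reader might infer that the Part B conclusions as a whole are undermined. They are not: the protocol plans no formal comparison, and the descriptive summaries and the power model for dose proportionality do not depend on this ANOVA.

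**What to change.** - Restrict the contrasts versus Part A to 180mg, as in protocol 9.4.2.2. The 90mg and 360mg data stay in the descriptive summaries and the power model.
- Drop the Y/Dose and Y/(BW x Dose) repeats of the ANOVA. If a pooled-dose comparison was intended, state that model, with a participant random effect because each Part B participant receives two doses.
- Replace the screen with two pre-specified 180mg models: the protocol's unadjusted ratio as the main result, and one named weight-adjusted model always reported as a sensitivity analysis.
- Reconcile the Day -1 labels for weight and height with the protocol's Screening measurement.
- Record the departures in SAP 6.4.

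The cost is SAP wording: fewer tables, one extra fixed model and no new data. Adjustment costs a little precision. With d = ln(75/(75 - gap)) and log-weight variance ln(1 + 0.15^2) = 0.0223, weight imbalance multiplies the SE by sqrt(1 + d^2/(49 x 0.0223)/(1/8 + 1/36)). This is 1.01 at 5kg and 1.14 at 15kg. After allowing for the residual variance that weight explains (b = 0.75 to 1), the net change is about -4% to -1% at 5kg and +9% to +12% at 15kg.
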